6.2.2 Complex prevention

Consists of a gentle toothbrush cleaning, oral hygiene instruction, an examination, delivery of glass ionomer sealants to all pits and fissures on bicuspids or molar teeth, and to all asymptomatic carious lesions. Each child is given a small bag with a toothbrush, fluoride toothpaste, and a note indicating the results of the examination, the care provided, and a list of local dentists or community health centers for follow on care.

6.3 Study Administration and Duration

Examination and care will be provided based in the school, at a community-based location, or NYUCD schedule and allow for a 30-minute eating free time following our care. Care is delivered in a school room (e.g.: an empty room or class room, auditorium stage, nurse office, etc.), at a community-based location, or at NYUCD using mobile dental equipment and disposable supplies.

The clinical treatment room set up will vary based on room size and ability to provide care at a safe distance. If the clinical room is small, only 1 station will be set up to provide care to 1 child at a time. If the clinical room is large (eg: auditorium stage or large empty room), individual stations (up to 3) will be set up and spaced at a minimum of 6' apart.

The room is set up prior to the beginning of treatment.

All clinical personnel will wear personal protective equipment consistent with CDC, DOH, FDA and NYU Dentistry guidelines.

NYUCD licensed dentists, dental hygienists, nurses, and/or advanced dental hygiene students supervised by licensed dental professionals will provide care to participating students at all locations. All clinical personnel providing care will wear PPE based on current NYU Dentistry guidelines. PPE is listed below:

- 1. Disposable gowns
- 2. Disposable gloves
- 3. N95 respirator that have been fit tested for a specific respirator and shall be disposed of at the end of each clinical day
- 4. Level 3 surgical masks
- 5. Goggles
- 6. Face Shields
- 7. Bonnets
- 8. Booties

Gloves are changed between patients. All dental chairs, stools and touch surfaces are disinfected with an EPA registered intermediate level surface disinfectant at the beginning of each day, prior to and after treating patients, and at the end of the day. Goggles and face shields are also disinfected between patients.

Care is delivered only during school, community-based location, or NYUCD hours. Based on informed consents, children will be scheduled and seen in a school room, a community-based location room, or at NYUCD. Children are escorted to the waiting room in the school by the school's parent coordinator. Children are brought by the parent/guardian at a community-based setting or at NYUCD. After the child and parent/guardian at the community-based location passes the COVID-19 screening test, the child will be escorted to the clinical treatment room by the dental assistant at all locations.

Care will be provided by NYUCD licensed dentists, dental hygienists, nurses, and/or advanced level dental hygiene students supervised by licensed dental professionals to all participating students at all locations. After the child has completed treatment they will be required to put their mask back on and apply an alcohol-based hand sanitizer. The dental assistant will bring the child to the waiting room area. The child will be escorted back to the classroom by the school's parent coordinator or back home by the parent/guardian from the community-based, or NYUCD locations.

Simple prevention takes approximately 5 minutes and is aerosol free. It consists or a gentle tooth brush cleaning, oral hygiene instruction, an examination, delivery of silver diamine fluoride which takes approximately 1 minute to apply using Advantage Arrest Applicators to all pits and fissures on bicuspids or molar teeth, and to all posterior, asymptomatic carious lesions. Fluoride varnish is then applied which also takes 1 minute to apply.

Complex prevention takes approximately 20 minutes and is aerosol. It consists or a gentle toothbrush cleaning, oral hygiene instruction, an examination, delivery of glass ionomer sealants to all pits and fissures on bicuspids or molar teeth, and to all asymptomatic carious lesions. This takes about 5 minutes to provide care to ¼ of the mouth at a time. Fluoride varnish is then applied which takes approximately 1 minute.

6.4 Control/Comparison Group and Confounding Factors

Complex prevention is the "comparison" while simple prevention is the "intervention" group. Both groups receive primary and secondary prevention and we expect both protocols to be similarly effective in reducing untreated caries.

We will include relevant confounders a priori in our analysis, including: gender, previous (or concurrent) dental treatment (identified as new or existing treated dentition at examination), age at examination, race/ethnicity, and any school-level indicators. As these data have a multilevel structure, we will additionally assess caries incidence and prevalence using multilevel mixed effects Poisson and logistic modeling (ML-MEM). We will examine the effects of comprehensive prevention at multiple levels (tooth, child, grade, and school). In this analysis, we will be able to explore the variation in clinical outcomes across child and school levels. For all GEE and multilevel models, we will conduct analysis for outcomes (caries prevalence and incidence) measured by all teeth, all adult teeth only, and all deciduous teeth only.

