The study administrator will then cross-reference the OSIS number in the original .csv file which was provided to us at the beginning of each school year by the NYC Department of Education, and verify that the correct OSIS number was provided correctly by the consenter.

The study administrator then uploads all of the informed consent PDF's to NESS via the secure and password protected ShareFile link listed below:

• https://nedental.sharefile.com

NESS then uploads each student's eICF to their electronic dental record in the iPad.

Examination, preventive care, and data collection by a proprietary secure electronic health record will be provided and collected up to 5 years, and all children in a given school will receive the same preventive care at the same frequency either at the school, at a community-based location or at NYUCD. Participants in their first and second years will contribute data to evaluate caries arrest, and then they will be followed longitudinally within schools. 50% of children ≥ 8 years old will be assessed with a validated quality of life instrument, and all children will receive a comprehensive oral examination at each visit. We will also test the secondary hypotheses that prevention: improves school performance and is equally effective given once per year as twice per year.

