6.1.6 Examination and Diagnosis

Each program will use password-protected Apple iPads with electronic dental records pre-populated with demographic information of all students with informed consent. Student lists on the Apple iPads will be used to: collect students during the care delivery days; record clinical findings and care delivered; and generate take home forms (see below). On the scheduled care days, we will provide a gentle toothbrush cleaning, oral hygiene instruction, a toothbrush and fluoridated toothpaste. We will also carry out an examination and provide preventive care.

The examination will include a soft tissue inspection and an assessment of all primary and permanent teeth to determine the presence/ absence of decay (active or arrested), missing, filled, or sealed surfaces on all teeth.

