6.1.7 Prevention

Both simple and complex care regimens provide both primary and secondary caries prevention. The goal of primary prevention is to prevent or delay the initial carious lesion using: 1) fluoride varnish for smooth surfaces (simple and complex prevention); and 2) either silver diamine fluoride (simple prevention) or sealants (complex prevention) for pits and fissures. The goal of secondary prevention is to arrest caries *in situ*, and prevent disease progression. This is accomplished with silver diamine fluoride (simple prevention) or interim therapeutic restorations (complex prevention).

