6.5.2 Blinding

As a pragmatic trial, this is non-blinded for the participants. Neither schools, nor teachers, nor students, nor clinicians will be blinded. Clinicians will work in teams that only provide either simple or complex prevention. The analysts will be blinded as to the care provided to students in a particular school.

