6.6 Compliance Assessment

This intervention trial depends on protocol compliance by clinicians, not students. We will train and calibrate clinicians during the summer before beginning each school year. To assess compliance, we will use qualitative and quantitative methods together with audit and feedback. Qualitatively, to ensure that the electronic records reflect actual implementation, we will visit each team in the fall and spring of each year for a one-day site visit. During the day, we will monitor adherence to protocol, particularly: student flow, caries diagnosis, and procedures delivered.

Quantitatively, we will use the elementary methods of statistical process control^{27,28}. We will examine four domains: 1) informed consent rates; 2) caries prevalence (e.g.: diagnosis); 3) care provision; and 4) outcomes. We will monitor these domains using electronic records and then verify with in-person site visits. We will start with national averages and standard deviations for school-based informed consent rate (35%), untreated caries prevalence of (21.5%). All children (100%) with permanent bicuspids and molars should receive either silver diamine fluoride (simple prevention) or traditional sealants (complex prevention) and fluoride varnish. All children (100%) with caries on their posterior teeth should receive either silver diamine fluoride (simple prevention).

We will create histograms, Pareto charts, and control charts, at the school, grade, and clinician level to identify common cause and special cause variation. Control limits will be adjusted yearly based on prior year data. If a clinician, school or grade exhibits variation that is out of the control range we will use this audit to work with the clinical team and school to provide feedback. We will continue this process during the school year.

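### Section 6.4 adjusts for concurrent, newly treated teeth without excluding the sealants and restorations that the study itself places only in the complex arm

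*Combined protocol and SAP*

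**What the plan says.** Section 6.4 lists the confounders to be included a priori. Beside gender, age, race/ethnicity and school-level indicators it names "previous (or concurrent) dental treatment (identified as new or existing treated dentition at examination". The same section then turns to the GEE and multilevel models of caries prevalence and incidence. Section 7.2 describes the GEE models for new caries but names no covariates for them.

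On measurement, 3.1 says that "all children will receive a comprehensive oral examination at each visit". Section 6.1.6 has each examination record "decay (active or arrested), missing, filled, or sealed surfaces on all teeth", and has the tablets "record clinical findings and care delivered".

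On study treatment:
- 6.1.7 arrests existing caries with "silver diamine fluoride (simple prevention) or interim therapeutic restorations (complex prevention".
- 6.2.2 defines complex care as including "delivery of glass ionomer sealants to all pits and fissures on bicuspids or molar teeth, and to all asymptomatic carious lesions". Simple care in 6.2.1 uses silver diamine fluoride and varnish, with no sealants or restorations.
- 6.6 sets a 100% target: every child with permanent bicuspids and molars "should receive either silver diamine fluoride (simple prevention) or traditional sealants (complex prevention) and fluoride varnish".

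On other care, 5.5 says that prior therapy is noted at examination, that children are referred to local dentists, and that about 10% of parents follow through. Section 6.7 is marked not applicable. Section 7.3 promises analysis as randomized.

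**The concern.** A covariate in a randomized comparison should be fixed before treatment starts, or at least be unaffected by it. The words for concurrent and new treatment reach beyond the child's state at entry, and no section says whose treatment counts. A sealant or interim restoration placed by the study at one visit is a sealed or filled surface at the next. Study care produces such surfaces in one arm only.

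A model holding that covariate constant no longer estimates the as-randomized contrast of 7.3. It compares simple-arm children with complex-arm children of like treated status, when that status is partly what the complex protocol delivers. Two opposite distortions are possible:
- Study restorations mark high-risk children in the complex arm only. Adjusting for them makes simple care look worse.
- Study sealants carry part of the complex arm's protection. Adjusting for them removes that protection from the comparison and makes simple care look better.

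**Working it through.** **1. Is the covariate limited anywhere?** Sections 3.1, 5.5, 6.1.6, 6.1.7, 6.2, 6.4, 6.6, 6.7, 7.1, 7.2 and 7.3 were read for a limit to the first examination, a limit to outside care, or an instruction to leave out study-placed work. None has one.

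**2. The plan's own figures.** None describes this covariate. The nearest is the arrest sample size in 7.1, which reproduces: 198 per group with one-sided alpha of 5%, 396 in total; design effect 1 + (235 - 1) x 0.10 = 24.4; 396 x 24.4 = 9,662. The point does not rest on it and the fix does not change it.

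**3. Direction.** Take a linear model of new caries on arm and a treated-teeth flag. Let f_S and f_C be the shares flagged in the simple and complex arms. Let b be the flag coefficient, which averages the within-arm risk differences (flagged minus unflagged) with weights f(1 - f) when the arms are of equal size. Then

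adjusted (simple - complex) = crude (simple - complex) + b x (f_C - f_S).

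With no true difference the second term is the bias. It vanishes when f_C = f_S, as when only outside care is coded and its uptake is equal. If study work is coded, f_C exceeds f_S, and the sign is that of b: positive when the flag marks risk, negative when it marks protection.

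**4. A hand case for the negative direction (all inputs assumed).** Outside care flags 10% in each arm, using the figure in 5.5, and is unrelated to risk. A sealant is seen in a share s of complex-arm children and halves an untreated risk r. Simple has the same average risk. Then f_S = 0.10, f_C = s + 0.10(1 - s), and the complex within-arm difference is -0.5 x r x s / f_C.

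- r = 0.20, s = 0.30: f_C = 0.37; difference = -0.081; weights 0.37 x 0.63 = 0.2331 and 0.10 x 0.90 = 0.09; b = -0.081 x 0.2331 / 0.3231 = -0.0585; bias = -0.0585 x 0.27 = -0.016, or -1.6 points.
- r = 0.35, s = 0.50: f_C = 0.55; difference = -0.159; weights 0.55 x 0.45 = 0.2475 and 0.09; b = -0.159 x 0.2475 / 0.3375 = -0.117; bias = -0.117 x 0.45 = -0.0525, or -5.25 points.

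**5. Simulation with the GEE models of 7.2.** 120,000 children per combination, equally effective arms, separate flags for existing and new treatment. Taken from the protocol: 40% baseline caries, 10% outside follow-through, an average of 6 visits, exchangeable correlation. Assumed: one baseline and five follow-up examinations, new caries in 10-30% per interval (untreated risk 20-35% in the protective-sealant row), existing treated dentition 30%, shared-risk loading 0.5-1.0 on the logit scale, and all coding shares below. Bias is adjusted minus unadjusted risk difference per interval.

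| What the covariate counts | Bias, simple minus complex (points) |
|---|---|
| Outside care only | -0.05 to +0.05 |
| Also study restorations, for 50-100% of complex-arm caries episodes | +0.3 to +3.4 |
| Also sealants, seen in 30-50% of complex-arm children | +0.4 to +3.1 |
| A coded sealant carrying 50% protection, seen in 30-50% | -1.3 to -5.2 |
| First-examination status only | within 0.06 of zero |

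The hand case agrees with the fourth row in sign and closely in size.

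**6. A second, one-visit simulation.** 400,000 children, equally effective arms, about 11% outside care in each. With study work coded in 100%, 90% and about 70% (risk-dependent) of complex-arm children, the bias was +6.0, -3.0 and -0.7 points. Adjusting for first-examination status gave log odds ratios of -0.006, -0.006 and +0.001. The formula in step 3 explains the +6.0. At full coverage f_C(1 - f_C) = 0, so b comes only from outside care in the simple arm, which in that simulation higher-risk children sought more often: b = (0.0597 + 0.0011) / (1 - 0.108) = 0.068.

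**7. What these runs cannot show.** The sizes in steps 5 and 6 do not agree, because they follow the assumed coding shares. The 50% sealant protection is an assumption: the 50-80% in 1.4.3 is a whole-programme figure, and Table 1 gives 80% for sealants on pits and fissures. No retention figure supports 30-50%. Neither school clustering nor the 20% per-visit attrition of 7.1 is modelled, so these are point biases, not error rates.

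**The case against.** The strongest reply is that the authors meant outside care. They call the variable a confounder, and its wording parallels 5.5, where prior therapy is followed by referral to local dentists. Study sealants are the assigned intervention, not treatment alongside it. A flag near 100% in one arm would also tend to unmask analysts of whom 6.5.2 says "The analysts will be blinded as to the care provided to students in a particular school". This reading is plausible, and under it the bias is about zero. It stands as a limit on the harm, but the limitation is not written down, and an unwritten intention does not bind whoever codes the variable.

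A reader might infer that blinded analysts could not remove study-placed work. The documents do not support that. Sections 8.4.1 and 8.11 route examination and care data through the data centre before analysis, so a rule could be applied there. What is missing is the rule.

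A reader might also set the shifts against the 10% margin. Sections 7.1 and 7.2 state that margin for arrest. None is stated for prevention, so nothing can be said about the chance of a wrong non-inferiority conclusion, and no claim is made about arrest.

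Finally, limiting the covariate to non-study care would also remove the bias if outside uptake is equal in the arms. That is true, but it requires attributing each treated surface to its provider, and 6.1.6 does not say that care delivered is recorded by tooth or surface.

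**Conclusion.** The point holds as a defect in a stated rule. Followed literally, 6.4 conditions the comparison of new caries on something that the complex protocol itself produces. That the wording permits this is certain from the text; that it would be coded so is not. The bias is about zero if only outside care is coded with equal uptake in both arms. It can take either sign if study work is coded. The illustrations span -5.2 to +6.0 points, and none is an estimate for this trial. The stronger inference, that the planned prevention analysis is biased, is not supported, because the documents give no coding rule. The change is worth making because it costs little and removes the dependence on a coding choice made later.

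**What to change.** In 6.4 and 7.2, define the treatment covariate in the primary simple-versus-complex caries models as treated dentition present at the child's first study examination, before any study care. Take concurrent and new treatment out of those models. The boundary should be the child's first examination and not randomization, since schools are randomized first and 6.1.1 lets children join each year.

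Report later treatment descriptively by arm, separating study-placed from outside care as far as the care-delivered record allows.

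The cost is wording and one derived variable from examinations already recorded; no sample-size figure changes. The small loss is adjustment for outside care received during follow-up. It can be kept as a sensitivity analysis limited to non-study care, with the identification rule written beforehand.

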6.5 Randomization and Blinding

6.5.1 Randomization

We will do a block randomization, generating sets of unique numbers to assign the experimental condition. Thus, for the first 30 schools we will generate 15 sets, each set containing a 1 or a 2, representing treatment assignment, in random order. We will repeat this in year 2 for the second set of 30 schools. In year 2, an additional 16 schools will be selected to receive simple prevention once per year.

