3.1 General Design

This is a pragmatic cluster randomized non-inferiority controlled trial comparing the clinical effectiveness of two caries prevention protocols. The study consists of three groups. Two groups will be randomly assigned at the school level to receive either simple or complex prevention provided twice yearly. A third group will be selected to receive simple prevention only, provided once yearly.

A total of 76 elementary schools will be selected from interested schools in New York City, identified via letters and phone calls to school principals. For groups (1) and (2) 30 elementary schools will be randomized to receive simple prevention twice per year and 30 elementary schools will be randomized to receive complex prevention twice per year. For group (3), 16 elementary schools will be selected to receive simple prevention once per year.

Beginning in the first year of the study, a total of 30 schools will be randomized (15 schools receiving simple prevention and 15 receiving complex prevention) to receive prevention twice per year consenting children will be followed over five years. In Year 2, 30 additional schools will be randomized to receive either simple or complex prevention twice per year. Consenting children will be followed over four years. Also in Year 2, an additional 16 schools will be selected to receive simple prevention once per year, and consenting children will be followed over four years. Also in Year 2, an additional 16 schools will be selected to receive simple prevention once per year, and consenting children will be followed over four years. Starting in year 3, all care will be provided by NYUCD HCP, in school, at community-based locations, or at NYUCD. Starting in year 5, NYUCD licensed dentists, dental hygienists, nurses, and/or advanced level dental hygiene students supervised by licensed dental professionals will provide care to participating students, in school, at community-based locations, or at NYUCD.

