4.2.2 School Randomization

Beginning in the first year of the study, a total of 30 schools will be randomized (15 schools receiving simple prevention and 15 receiving complex prevention) to receive prevention twice per year. Consenting children will be followed over five years. In Year 2, 30 additional schools will be randomized to receive either simple or complex prevention twice per year. Consenting children will be followed over four years. Also in Year 2, an additional 16 schools will be selected to receive simple prevention once per year, and consenting children will be followed over four years.

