7.2 Statistical Methods

For caries arrest, we will first determine the per-patient proportion of carious lesions treated with simple versus complex prevention that stayed arrested throughout the length of the study. The percentage of arrested caries (at the child level) will be modeled using multilevel binomial regression. Our noninferiority margin, δ , is set at 10%. Our null hypothesis is that simple prevention is not inferior to the complex prevention by at least δ : π_{simple} - $\pi_{\text{complex}} \ge \delta$. Our alternative hypothesis is that π_{simple} - $\pi_{\text{complex}} < \delta$. We will use differences in effect sizes as estimated by confidence intervals to determine clinical non-inferiority of the two prevention methods. For the prevention of new caries, we will use generalized estimating equations (GEE) with a logit link (caries prevalence) and a negative binomial link (caries incidence), assuming an exchangeable correlation matrix, to evaluate longitudinal effects of comprehensive care untreated decay. We will identify the number of teeth at risk for each child during each follow-up interval and determine the number of those teeth in which new caries is observed at the examination that ends that interval. Primary teeth lost in each interval and new permanent teeth will not contribute to data for that interval. To explore non-linear trends in untreated decay between simple and complex prevention, we will use generalized additive models (GAMs) with non-parametric smoothers. Longitudinal effects of simple and complex prevention on academic outcomes, compared to untreated children, will be analyzed using propensity score-matching and multilevel modeling. First, we will estimate propensity scores for each participant at baseline, establishing the probability of treatment assignment conditional on observed covariates (e.g., prior academic performance). Propensity scores will be used to match treatment students to students not receiving treatment, considering multiple forms of matching
such as nearest neighbor and caliper. Treated students and matched comparators will then be analyzed using multilevel mixed effects linear regression (for academic achievement) and Poisson regression (for school absences).

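### Schools are randomised 15:15 within each of two yearly waves, but wave is not pre-specified by name in the arrest or prevention models

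*Combined protocol and SAP*

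**What the plan says.** Section 6.5.1 allocates schools in blocks of two: "for the first 30 schools we will generate 15 sets, each set containing a 1 or a 2". It then adds: "We will repeat this in year 2 for the second set of 30 schools". Section 3.1 agrees on the timing: "In Year 2, 30 additional schools will be randomized to receive either simple or complex prevention twice per year". Both waves are therefore split 15 simple to 15 complex. Children in wave 1 are followed for five years; for wave 2, Section 4.2.2 says "Consenting children will be followed over four years".

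For arrest, Section 7.2 says "The percentage of arrested caries (at the child level) will be modeled using multilevel binomial regression" and names no covariates. For prevention it specifies GEE with logit and negative binomial forms, "assuming an exchangeable correlation matrix, to evaluate longitudinal effects of comprehensive care untreated decay", again with no term for wave, year of entry or calendar year.

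The covariates are in Section 6.4: "We will include relevant confounders a priori in our analysis, including: gender, previous (or concurrent) dental treatment", and later in the same sentence "age at examination, race/ethnicity, and any school-level indicators". The last item is not defined. Wave is an attribute of the school, so it could fall under that item, but nothing says that it does. Section 6.9 mentions stratification ahead of randomisation without defining any strata.

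**The concern.** Because each arm has 15 schools from each wave, a difference between waves cancels out of the treatment contrast. An analysis that ignores wave still counts that difference as unexplained variation between schools. The reported standard error then exceeds the true sampling error, the confidence interval is too wide, and the non-inferiority test rejects less often than its nominal level.

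The plan gives reasons why the waves might differ. School closures, the move to other care sites from study year 3 and the change in provider types from year 5 (Sections 3.1 and 6.9) reach the two waves one follow-up year apart. Children who enter in the first year of wave 2 come to the two-year arrest endpoint of Section 3.2 about one study year later than their wave 1 counterparts. Whether this produces a difference in outcome, and of what size, is not stated.

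At stake are some precision and some analyst discretion: with the school-level item undefined, the decision to adjust for wave can be taken once data are in hand.

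**Working it through.** **Step 1: the plan's own figure.** Section 7.1 gives 20% arrest in both arms, a margin of 10 points, alpha 5%, power 80%, ICC 0.10 and 235 children per school.

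- n per arm = (1.645 + 0.842)² × 2 × 0.20 × 0.80 / 0.10² = 6.18 × 32 = 198.
- Design effect = 1 + (235 − 1) × 0.10 = 24.4.
- Total = 396 × 24.4 = 9,662.

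This reproduces the plan. It needs alpha to be one-sided 5%; one-sided 2.5% would give 252 per arm and 12,298 in total. One-sided 5% is used below.

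**Step 2: school-level comparison, 30 v 30 schools.** Total variance = 0.20 × 0.80 = 0.16. Between schools: 0.10 × 0.16 = 0.016. Within schools: 0.144. Variance of a school mean = 0.016 + 0.144/235 = 0.01661. SE of the difference = √(2 × 0.01661/30) = 0.0333.

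**Step 3: wave.** Two equal waves whose mean arrest differs by D contribute D²/4 to the between-school variance. Total between-school variance is held at 0.016.

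- With a wave term: SE = √(2 × (0.016 − D²/4 + 0.144/235)/30).
- Without it: the within-arm variance keeps the wave part, as (30/29) × D²/4, so SE = √(2 × (0.016 − D²/4 + 0.144/235 + (30/29) × D²/4)/30).
- The true sampling SD of the estimate is the first expression in both cases.

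For D = 0.10, D²/4 = 0.0025. With the term: √(2 × 0.01411/30) = 0.0307. Without: √(2 × 0.01670/30) = 0.0334. The ratio is 0.92, so the SE is 8% smaller.

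**Step 4: results.** D is assumed, because the documents give no value. True treatment difference is zero for power; t-test on 58 df without the term and 57 with it (critical values 1.6716 and 1.6720).

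| D (points) | SE without | SE with | Reduction | Power without | Power with | Type I error without (nominal 5%) |
|---|---|---|---|---|---|---|
| 0 | 0.0333 | 0.0333 | 0% | 90.6% | 90.7% | 5.0% |
| 5 | 0.0333 | 0.0326 | 2% | 91.0% | 91.6% | 4.7% |
| 10 | 0.0334 | 0.0307 | 8% | 92.3% | 94.3% | 3.7% |
| 15 | 0.0335 | 0.0271 | 19% | 94.5% | 97.8% | 2.2% |

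The 0.1-point power difference at D = 0 is approximation error, not a gain. Power rises with D in both columns because the total between-school variance is held fixed. A simulation with 40,000 trials per setting gave the same pattern (at 10 points, 92.5% v 94.3%).

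**Step 5: sensitivity.** If only children with caries at baseline count for arrest (40% of 235 = 94 per school), a 10-point wave difference gives SEs of 0.0343 and 0.0317 and power of 90.9% and 93.0%. With ICC 0.05 and 235 per school, the SEs are 0.0241 and 0.0202, and power is above 99% either way.

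**Step 6: can omission bias the estimate?** Not in the balanced school-level comparison, where adding wave leaves the estimate unchanged. Child-level models give weight to the number of children analysed, so 15:15 schools do not guarantee balanced children. As an illustration, if wave 2 supplied 50% of analysed children in one arm and 40% in the other, a 10-point wave difference would create a spurious difference of up to (0.50 − 0.40) × 10 = 1 point. All three figures are assumed.

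**The case against.** The strongest reply is that Section 6.4 already commits to school-level covariates and that wave is one. This stands in part: the documents do not show that wave is excluded. They show only that it is not named.

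The second reply is that a large wave difference is speculative. Both waves use the same entry criteria (at least 50% Hispanic/Latino, at least 80% free or reduced lunch), in one city, one year apart. A 15-point gap around 20% would mean about 12.5% v 27.5% arrest. This also stands. A reader might infer a guaranteed gain in precision, but the documents supply no wave difference from which to claim one.

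Third, the primary endpoints in Section 3.2 fall at two and three years, within planned follow-up for both waves, so the five-year v four-year contrast matters less than it seems. Section 7.2 does describe arrest as lasting for the whole study, which makes length of follow-up relevant, but that is a conflict over the endpoint definition that a wave term does not resolve.

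Fourth, the calculation is linear and at school level, whereas the planned models are binomial, logit and negative binomial. The percentages do not carry over directly. In a logit model, adjustment changes the conditional odds ratio and need not shrink its standard error; the gain belongs to the risk difference, which is the scale of the margin.

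A reader might also infer that leaving wave out biases the comparison or favours a false claim of non-inferiority. The documents do not support that. The error runs in the conservative direction, and the small bias in Step 6 needs an uneven spread of analysed children over waves between arms, of which the plan gives no sign.

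**Conclusion.** The point holds as a missing pre-specification: a restriction built into the randomisation is not carried by name into the primary models. Its consequence is lost precision and a conservative test. The loss is nil if the waves do not differ, slight at 5 points, and noticeable only from about 10 points upward. These sizes rest on the plan's 20% arrest, ICC 0.10 and 235 children per school, a one-sided 5% test, equal school sizes, and wave differences that are assumed throughout. With power above 90% on the plan's inputs even without the term, the primary conclusion is not at risk. The change is worth making because it costs almost nothing and settles the adjustment in advance: a free improvement, low to moderate priority.

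**What to change.** In Section 7.2, state that randomisation wave (Year 1 or Year 2) enters the primary arrest and prevention models as a fixed effect. Add that non-inferiority against the 10-point margin will be judged on a standardised (marginal) risk difference with its confidence interval, not on a conditional odds ratio.

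The cost is one sentence on each, a variable that already exists, and one degree of freedom (58 to 57 in the school-level comparison).

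Optionally, add a categorical calendar-year or wave-by-visit term to the longitudinal prevention models. A wave main effect removes only the average difference between waves; closures and changes of setting during follow-up need a time term as well. A linear time term would not capture an abrupt change, and the categorical form costs a few more parameters.
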